#### **Definition of the MTD**

The MTD is defined as the highest dose level of VK-2019 at which fewer than two DLTs are observed in six evaluable dose escalation patients at that dose level.

#### **Definition of a BCAD**

A BCAD is defined as any dose level that appears to have preliminary clinical or biological activity based upon the following criteria:

- There are no safety concerns in that cohort based upon the SRC's analysis of safety data.
- The following criteria for either clinical or biological activity:

Clinical:

• At least one dose escalation patient has experienced an objective response per RECIST v1.1 (i.e., a PR or CR) at that dose level.

#### **Biological**:

- Post-baseline plasma EBV DNA levels have declined by three log from baseline, or are below the lower limit of detection of the assay, AND,
- Plasma AUC level VK-2019 at the end of Cycle 1 is above the biologically active dose as defined in preclinical models (10,000 ng\*h/mL).

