	
 
within three days, and is not associated with hemodynamic compromise (including hypotension, or clinical or laboratory evidence of end organ perfusion impairment)
 
o Grade 3 diarrhea, nausea, vomiting, or abdominal pain that returns to Grade 1 or baseline within three days with medical intervention
 

Protocol VK-2019-001	Version 9.0, 15-October-2019
	• Grade 3 pruritis or rash that returns to Grade 1 or baseline within
	seven days or baseline with medical intervention
	• Grade 3 fatigue
	• Grade 3 tumor flare (defined as pain, irritation or rash that
	localizes to sites of known or suspected tumor)
	1 /
	A DLT will also include:
	• A laboratory finding of acute liver injury defined as:
	• Sustained (> 1 week) doubling of AST or ALT levels to no less
	than 4 x ULN, or sign of increasing functional liver impairment
	with $> 2x$ baseline increase in total bilirubin
	
 
Increased AST or ALT levels above 8 x ULN
 

	• Suspected acute liver injury (per Hy's law) $ALT/AST > 3 \times ULN$
	in combination with Total Bilirubin $> 2 \times ULN$ in the absence of
	cholestatic injury (ALP $< 2 \text{ x ULN}$ ).
	• Any AE resulting in a patient missing > 7 days of dosing with VK-
	2019
	• Any AE not otherwise meeting the criteria or timing of a DLT as
	defined above, but is declared a DLT by the SRC
Definition of the	The MTD is defined as the highest dose level of VK-2019 at which
MTD:	fewer than two DLTs are observed in six evaluable patients treated at
	that dose.
Definition of a	A BCAD is defined as a dose level that appears to have preliminary
BCAD:	clinical or biological activity based upon the following criteria:
	• There are no safety concerns in that cohort based upon the SRC's
	analysis of safety data.
	• The following criteria for either clinical or biological activity:
	Clinical:
	• At least one patient has experienced an objective response per
	RECIST v1.1 (i.e., a PR or CR) at that dose level.
	Biological:
	• Post-baseline plasma EBV DNA levels have declined by three
	log from baseline, or are below the lower limit of detection of the
	assay, AND
	• Plasma AUC level VK-2019 at the end of Cycle 1 is above the
	biologically active dose as defined in preclinical models (10,000
Definition of the	ng*h/mL) The dasa of orally administered VK 2010 monotherapy that in the
RP2D	The dose of orally administered VK-2019 monotherapy that, in the
NI 4D	opinion of the SRC, can be safely administered for three or more

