	cycles, factoring in cumulative adverse experiences and adverse
T 1/1 /1 ATT -	experiences that lead to study drug discontinuation.
Initiation of Phase 1	The SRC may elect to initiate a Phase 1 Dose Expansion Cohort and
Expansion Cohorts:	enroll additional patients at any dose level that:
	• Meets the definition of the MTD.
	• Meets the definition of a BCAD.
	The total number of patients enrolled at any one dose level during Phase
	1 (dose escalation and expansion) will not exceed 16 patients.

	Based upon the above criteria, the SRC may elect to explore multiple dose levels as Phase 1 Expansion Cohorts (either staggered or concurrently).
Initiation of Dhase	
Initiation of Phase	Upon completion of any Phase 1 Expansion Cohort, the SRC may elect
2a Expansion	to expand the cohort further, initiating a Phase 2a Dose Expansion and
Cohorts:	enrolling additional nine patients if the dose level meets the following:
Conorts.	
	• Two or more patients have experienced an objective response per
	RECIST v1.1 (i.e., a PR or CR), of which at least one is a confirmed
	response.
	• There are no additional safety concerns in the cohort of existing
	•
	patients based upon the SRC's analysis of emerging safety data.
	The total number of patients enrolled at any one dose level during all
	phases of the study will not exceed 25 patients.
	Based upon the above criteria, the SRC may elect to explore multiple
	dose levels as Phase 2a Expansion Cohorts (either staggered or
~	concurrently).
Study Population:	Inclusion Criteria:
	A patient who meets all of the following inclusion criteria will be eligible
	to participate in this study:
	1. Informed consent obtained prior to any protocol mandated
	assessment.
	2. Age $\geq$ 18.
	3. Either loco-regionally recurrent or metastatic EBV-positive
	nasopharyngeal carcinoma not amenable to curative treatment.
	a. EBV positivity is defined as high EBV viral load in plasma
	(> 4000 genomes per µg plasma DNA) and/or biopsy tissue
	positive for EBV.
	4. Prior palliative radiation must have been completed at least 2 weeks
	prior to study Cycle 1 - Day 0.
	5. Prior anti-cancer systemic treatment must have been completed
	greater than 4 weeks prior to study Cycle 1 - Day 0.
	6. Toxicities related to prior anti-cancer therapy must have returned to
	Grade 1 or less. Peripheral neuropathy must be Grade 2 or less.
	1 1 1
	Chronic but stable toxicities Grade > 1 (e.g., dysphasia, G tube

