### **III.** Study Information

### **Inclusion** Criteria

	Prospective Study Patient Must MATCH ALL these Inclusion Criteria to be Eligible	Yes	No	Supporting Documentation *
1.	Informed consent obtained prior to any protocol mandated assessment			
2.	Age $\geq 18$			
3.	Either loco-regionally recurrent or metastatic EBV-positive nasopharyngeal carcinoma not amenable to curative treatment. EBV positivity is defined as high EBV viral load in plasma (> 4000 genomes per $\mu$ g plasma DNA) and/or biopsy tissue positive for EBV			
4.	Prior palliative radiation must have been completed at least 2 weeks prior to study Cycle 1 – Day 0			
5.	Prior anti-cancer systemic treatment must have been completed greater than 4 weeks prior to the first dose of VK-2019			

	Prospective Study Patient Must MATCH ALL these Inclusion Criteria to be Eligible	Yes	No	Supporting Documentation *
6.	Toxicities related to prior anti-cancer therapy must have returned to Grade 1 or less. Peripheral neuropathy must be Grade 2 or less. Chronic but stable toxicities Grade > 1 (e.g., dysphasia, G tube dependence, etc.) may be allowed after agreement between the Investigator and Sponsor.			
7.	For the dose expansion phase in Phase 1 and Phase 2a: Patients must have RECIST v1.1 measurable disease, defined as at least one lesion that can be accurately measured in at least one dimension (longest diameter to be recorded for non-nodal lesions and short axis for nodal lesions) as $\geq 10$ mM with spiral CT scan, MRI, or calipers by clinical exam			
8.	ECOG performance status score of $\leq 2$ at study entry.			
9.	Absolute neutrophil count > 1500/µL (stable off any growth factor for at least 1 week of study drug administration)			
10	Hemoglobin > 9g/dL (transfusion to achieve this level is permitted )			
11.	Platelet count > 75 x 103/ $\mu$ L (transfusion to achieve this level is NOT permitted )			
12.	Serum aspartate transaminase (AST) and serum alanine transaminase (ALT) ≤ 2.5 x upper limit of normal (ULN)			
13	Total serum bilirubin $\leq 1.5 \text{ x ULN}$			
14	Serum creatinine $\leq 1.5$ x ULN or creatinine clearance $\geq 50$ mL/min as calculated per Cockcroft-Gault equation			
15	Urinary protein < 2+ by dipstick. If dipstick $\ge$ 2+, then a 24-hour urine collection can be done and the patient may enter only if urinary protein is < 1 g/24 hour			

		г	

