#### 6.1.1 During Phase 1 Dose Escalation

After completion of a dose escalation cohort, the SRC will convene to evaluate the safety, tolerability, PK, and, if available, PD data of VK-2019 from that cohort with the purpose of deciding upon the next dose level.

Upon reviewing data from that cohort, the SRC may decide to:

- Escalate to the next dose level
- Convert to the rolling-six dose escalation schema
- Enroll up to a maximum of 6 evaluable patients
- De-escalate to either a previously explored lower dose level (up to a maximum of 6 evaluable patients) or to an intermediate lower dose level
- Discontinue dose escalation in the trial
- Initiate a Phase 1 Dose Expansion Cohort
- Consider alternative dosing frequencies or intermittent dosing schedules
- Terminate the trial
- Defer their decision until additional data from patients in that cohort and/or other cohorts becomes available

Additionally, PK profiles for patients treated two dose levels below a dose level under consideration for escalation will be required by the SRC prior to starting a given dose level, e.g., Cohort 3 will begin only after PK information on Cohort 1 is available for review. If super-proportional PK is observed following the single-dose PK on C1D0, the dose of VK-2019 may be modified to account for the increase in exposure. If significantly less than dose proportional exposure is observed, dose escalation may be stopped and one of the doses with the highest exposure may be selected for expansion.

Any patient started on treatment in error, i.e., he/she failed to comply with all of the selection criteria, but still meets the criteria of an evaluable patient will be reviewed on a case by case basis by the SRC to determine if the patient should be included or excluded in the decision for dose escalation.

During the dose escalation, decisions made by the SRC will be documented and provided to the investigators prior to dosing any new patients.

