## **Dose Escalation Procedures**

The starting dose for VK-2019 is 60 mg QD. Sample dose escalation tables are below in Table 7, detailing a sample dose escalation schema based upon when escalation converts from Accelerated Titration to a Rolling Six design.

6.2.1 Definition of a Completed Cohort and an Evaluable Patient Each dose escalation cohort will consist of either:

- 1 evaluable patient (Accelerated Titration cohorts), or
- 3-6 evaluable patients (Rolling Six cohorts)

[figure not shown]
To be considered evaluable, a patient will have and one of the following:

- Received 75% of doses during Cycle 1, or,
- Received at least one dose of VK-2019 and experienced a DLT during Cycle 1
- 6.2.2 Dose Escalation in Accelerated Titration Cohorts

Upon completion of an accelerated titration cohort (Figure 2),

- IF: No VK-2019 related Grade ≥ 2 AEs occur during Cycle 1; THEN: Dose escalation may proceed to the next accelerated titration cohort (no greater than a 100% dose increase).
- IF: The patient experiences any VK-2019 related Grade ≥ 2 AE during Cycle 1 (not meeting the definition of a DLT); THEN: Convert the current cohort to the Rolling Six design and enroll an additional 2-5 patients (3-6 total).
- IF: The patient experiences a DLT; THEN: Convert to the Rolling Six design and enroll an additional five patients (six total).

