#### Initiation of Phase 1 Expansion Cohorts

The SRC may elect to initiate a Phase 1 Dose Expansion Cohort and enroll additional patients at any dose level that:

- Meets the definition of the MTD.
- Meets the definition of a BCAD.

The total number of patients enrolled at any one dose level during Phase 1 (dose escalation and expansion) will not exceed 16 patients.

Based upon the above criteria, the SRC may elect to explore multiple dose levels as Phase 1 Expansion Cohorts (either staggered or concurrently).

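### The EBV DNA limb of the BCAD rule has no baseline condition, so a patient undetectable at entry can meet it without any change; and the SAP lists the antiviral response rate but plans no tabulation of it

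*Protocol*

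**What the plan says.** **BCAD rule.** In the Protocol, Definition of a BCAD, the biological route has two parts, joined by AND. The viral part is met when "Post-baseline plasma EBV DNA levels have declined by three log from baseline, or are below the lower limit of detection of the assay"; the Synopsis has the same text ("log from baseline, or are below the lower limit of detection of the"). The exposure part requires an end-of-Cycle-1 AUC above 10,000 ng*h/mL. The committee must also see no safety concern in the cohort. The clinical route names a patient count ("At least one dose escalation patient has experienced an objective response per RECIST v1.1"). The viral part names none.

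**Eligibility.** Inclusion criterion 3 opens with "EBV positivity is defined as high EBV viral load in plasma", with a threshold of more than 4000 genomes per µg plasma DNA, and continues "and/or biopsy tissue positive for EBV". Tissue positivity is therefore enough by itself.

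**Endpoint and analysis.** Protocol 14.1.2 and 14.2.2 define the complete antiviral response as a drop below the lower limit of detection (LLOD). The section Pharmacodynamic EBV DNA calls it a reduction below the LLOD and says the partial and complete rates will be calculated. SAP 4.2 lists the rate as secondary in both phases. SAP 7.11 plans one output: a line graph of mean ± SD change from baseline by visit, for Phase 1 Dose Escalation only.

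**Assay.** The Protocol section on the effect of VK-2019 on plasma EBV DNA assigns testing to each institution's clinical laboratory. Later in the same section it assigns testing to a central laboratory with a harmonized assay.

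**The concern.** A criterion for biological activity should require that something changed. The three-log alternative does; the below-LLOD alternative does not. A patient enrolled on tissue positivity whose plasma EBV DNA is undetectable before and after dosing meets the viral limb as written, although nothing has been observed about the drug's effect on the virus.

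Two uses of the label are exposed. First, a BCAD is one of the two grounds on which the Safety Review Committee may open a Phase 1 Dose Expansion. Second, the rate and severity of treatment-emergent adverse events at the MTD and BCAD is a secondary endpoint (Protocol 14.1.2, SAP 4.2), so the label decides which doses are reported there.

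On the SAP side, a listed secondary endpoint has no table, denominator, confidence interval or rule for values below the LLOD. The reader of the report cannot tell whether it was dropped on purpose.

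**Working it through.** The point concerns wording and one missing analysis. No stated power or error rate depends on it.

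1. **The texts side by side.**
   - Definition of a BCAD and Synopsis: three-log fall, or a post-baseline level under the LLOD. The second alternative is a state, with no baseline condition.
   - Protocol 14.1.2 and 14.2.2: three-log reduction, or a drop under the LLOD. Both are changes.
   - Pharmacodynamic EBV DNA: reduction of three log or more, or reduction under the LLOD. Both are changes.

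   The BCAD text is the looser of the two, and the difference affects only patients who start below the LLOD.

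2. **Can a patient start below the LLOD?** Yes. Criterion 3 admits on tissue alone. The EBV DNA population (Protocol, Populations for Analyses; SAP 7.3) needs one dose and available biomarker data, not a detectable baseline.

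3. **Size, from the documents.** The planned total reproduces: 5 × 6 = 30 in escalation, 2 × 10 = 20 in Phase 1 expansion and 2 × 9 = 18 in Phase 2a, giving 30 + 20 + 18 = 68. The cap is "The total number of patients enrolled at any one dose level during Phase 1 (dose escalation and expansion) will not exceed 16 patients". With six patients already treated at the dose, as in the planning case, an expansion adds at most 16 − 6 = 10 patients.

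4. **Illustration only.** Let q be the share undetectable at baseline who stay undetectable. The documents do not give q, so 5%, 10% and 20% are assumed. The chance that a three-patient cohort meets the viral limb through such patients alone is:
   - if one patient suffices, 1 − (1 − q)³ = 14.3%, 27.1%, 48.8%;
   - if two of three are needed, 3q²(1 − q) + q³ = 0.7%, 2.8%, 10.4%.

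   A completed cohort may also be just "1 evaluable patient (Accelerated Titration cohorts), or"; the chance is then q itself. All of these are before the AUC and safety conditions. They show that the unstated patient count matters as much as q.

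5. **Denominator of the response rate.** Under the endpoint wording, a patient undetectable at baseline cannot be a responder but stays in the EBV DNA population. If the true rate among detectable patients is t, the reported rate is (1 − q)t. With t = 30% assumed and the same q, that is 28.5%, 27.0% and 24.0%.

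6. **SAP check.** SAP 7.11 gives the visits (C1D14, C2D0, C2D14, C3D0) but no scale, dose grouping or below-LLOD rule. No other SAP section tabulates the rate.

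**The case against.** The strongest reply is that the rule is contained. The BCAD definition speaks of a dose that seems to show preliminary activity, so a committee with the baseline values in hand need not treat an unchanged undetectable level as activity. The AUC and safety conditions must hold too. The committee may also "Defer their decision until additional data from patients in that cohort and/or other cohorts becomes available" or enroll more patients, and expansion is elective. A dose that meets the MTD definition can be expanded with no sign of activity at all. An expanded cohort stops if 16 patients yield one or no responses. All of this stands and limits the harm. It does not repair the text: AUC measures exposure, the safety condition measures safety, and neither tests for a viral change.

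A second reply is that the SAP serves an abbreviated CSR and trims silently elsewhere. Durable ORR, DOR, DCR, PFS and OS appear in SAP 4.1 but not in 7.13. Tmax and urine parameters are in the protocol's PK analysis but not in SAP 7.10. Shift tables are in the protocol but not in SAP 7.14.2. The explicit no-output statements (SAP 7.5, 7.12, 7.14.6, 7.14.7, 7.15) mark sections with nothing in them. This also stands: a reader might infer that the rate was forgotten, but silence does not show that. What remains is that the SAP neither carries the protocol's commitment forward nor says it is dropped.

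The SAP refers to biopsy collection in the past tense, which suggests that it was written late. If so, rewording the BCAD rule may no longer change a decision. The reporting part would still apply.

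**Conclusion.** The point holds and is minor to moderate in size. As written, the below-LLOD alternative can be met with no change in plasma EBV DNA, and it departs from the protocol's own endpoint wording. The practical risk is a Phase 1 expansion opened on a false biological signal, with at most 10 added patients in the planning case, and a dose wrongly labelled a BCAD for the adverse-event endpoint.

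The documents do not support stronger readings:
- **That one undetectable patient makes a dose a BCAD.** The AUC and safety conditions must also be met.
- **That a false efficacy claim could follow.** Phase 2a requires two RECIST responses, at least one of them confirmed.
- **That the illustrative percentages are chances of a false BCAD.** They rest on an assumed q and an assumed patient count, and they leave out the other conditions.
- **That undetectable baselines would inflate the antiviral response rate.** The endpoint text requires a drop or reduction, so these patients can only dilute it.

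The missing patient count and the laboratory conflict are secondary clarifications.

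**What to change.** 1. **Protocol, Definition of a BCAD and Synopsis.** Reconcile the wording with 14.1.2, 14.2.2 and the Pharmacodynamic EBV DNA section, so that the below-LLOD alternative counts only for a patient whose baseline plasma EBV DNA was at or above the LLOD. State how many patients must meet the limb; the number is for the sponsor to set.
2. **SAP 7.11.** Either tabulate the partial and complete antiviral response rates by dose level, with exact 95% confidence intervals among patients with a detectable baseline, and show change from baseline on the log10 scale with a stated below-LLOD rule; or say that the rate is omitted from the abbreviated CSR.
3. **Assay.** Reconcile the local-laboratory and central-laboratory statements so that one LLOD applies.

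The cost is wording, one table and a slightly smaller EBV denominator. The screening plasma EBV DNA sample is already scheduled in all three parts (Protocol Tables 1 to 3), so no new sampling is needed.

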#### Definition of the RP2D

The dose of orally administered VK-2019 monotherapy that, in the opinion of the SRC, can be safely administered for three or more cycles, factoring in cumulative adverse experiences and adverse experiences that lead to study drug discontinuation.

#### Initiation of Phase 1 Expansion Cohorts

The SRC may elect to initiate a Phase 1 Dose Expansion Cohort and enroll additional patients at any dose level that:

- Meets the definition of the MTD.
- Meets the definition of a BCAD.

The total number of patients enrolled at any one dose level during Phase 1 (dose escalation and expansion) will not exceed 16 patients.

Based upon the above criteria, the SRC may elect to explore multiple dose levels as Phase 1 Expansion Cohorts (either staggered or concurrently).

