# 1 SYNOPSIS

Study Title:	Phase 1/2a open-label, multicenter clinical trial of a novel small molecule EBNA1 inhibitor, VK 2019, in patients with Epstein Barr Virus
	positive nasopharyngeal cancer, with pharmacokinetic and
	pharmacodynamic correlative studies
Protocol Number:	VK-2019-001
Study Drug:	VK-2019
Sponsor:	Cullinan Apollo Corp
Hypothesis for	Plasma exposures of single agent VK-2019 associated with pre-clinical
Phase 1	efficacy can be achieved in patients with NPC with less than 18% of patients experiencing a dose limiting toxicity (DLT).
Hypothesis for	Oral administration of single agent VK-2019 at one or more doses will
Phase 2a:	be associated with a durable overall response rate (CR+PR maintained
	for at least 6 months) of 30%.
Objectives for	Primary Objectives
Phase 1:	
 
To define the maximum tolerated dose (MTD) and the recommended Phase 2 dose (RP2D) for orally administered VK-2019 monotherapy in patients with recurrent or metastatic NPC.
 
To evaluate and characterize the safety profile of orally administered VK-2019 monotherapy in adult patients with recurrent or metastatic
 

	NPC. Secondary Objectives
	• To evaluate the anti-tumor activity of orally administered VK-2019 monotherapy per Response Evaluation Criteria in Solid Tumors (RECIST) v1.1.
	• To characterize the PK of orally administered VK-2019 monotherapy in adult patients with recurrent or metastatic NPC.
	• To evaluate the anti-EBV activity by reduction of plasma EBV-DNA of orally administered VK-2019 monotherapy in adult patients with recurrent or metastatic NPC.
	Exploratory Objectives
	
 
To explore blood PD markers.
 

	
 
To explore PD markers such as alteration in EBV specific gene expression, both lytic and latent EBV genes.
 

	
 
To explore exposure-response relationships between VK-2019 exposure and the PD endpoints (safety, efficacy, and laboratory correlatives).
 

Objectives for	Primary Objectives
Phase 2a:	• Evaluate preliminary efficacy (overall response rate [ORR], duration of response [DOR], disease control rate [DCR], progression free survival [PFS], survival rate, and overall survival [OS]) of orally administered VK-2019 monotherapy in adult patients with recurrent or metastatic NPC.
	• Confirm the safety and tolerability of orally administered VK-2019 monotherapy in adult patients with recurrent or metastatic NPC.

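### A Phase 1 expansion to 16 can open through the BCAD route after one escalation patient, the expansion routes and MTD definitions conflict, and DLT incidence is never set against the 18% hypothesis

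*Protocol*

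**What the plan says.** **Routes to expansion.** Protocol 6.7: "The SRC may elect to initiate a Phase 1 Dose Expansion Cohort and enroll additional patients at any dose level that" qualifies as the MTD or as a BCAD, up to 16 patients at that dose in Phase 1, escalation patients included. Section 4 gives the same two routes. Section 6.1.1 adds that, if exposure rises much less than in proportion to dose, "dose escalation may be stopped and one of the doses with the highest exposure may be selected for expansion".

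**What a BCAD needs.** Protocol 6.5 requires that the SRC see no safety concern in the cohort, plus clinical or biological activity. The clinical criterion is: "At least one dose escalation patient has experienced an objective response per RECIST v1.1". No minimum cohort size is given. Section 6.2.1 defines a completed escalation cohort as "1 evaluable patient (Accelerated Titration cohorts), or" three to six in Rolling Six.

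**Assumed numbers.** Protocol 14.3 and SAP 5 assume 10 patients added at each expanded dose to reach 16.

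**MTD.** Section 6.4: the highest dose at which "fewer than two DLTs are observed in six evaluable dose escalation patients at that dose level". The Synopsis uses the same count but takes any six evaluable patients treated at the dose.

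**DLT rules and reporting.** The stop at two or more DLTs (6.2.3) is written for Rolling Six cohorts. Section 6.1.2 requires SRC reviews during and after each expansion, with power to stop enrolment or lower the dose; the SRC Charter holds when they occur and on what grounds. Protocol 14.5.1 and SAP 7.14 assess DLT incidence in All Treated.

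**Hypothesis.** The Synopsis states that exposures linked to preclinical "efficacy can be achieved in patients with NPC with less than 18% of patients experiencing a dose limiting toxicity".

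**The concern.** The number of patients behind the decision to expand can be far smaller than the sample-size section supposes. A reader cannot tell from the protocol which routes are open, whether DLTs in expansion patients count toward the MTD, or what cohort-level DLT count would matter once expansion has begun.

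Two things are at stake. One is patient safety at a dose known from one person. The other is the Phase 1 primary objective and hypothesis. Under 6.4 the MTD may stay undefined if no dose collects six escalation patients. The 18% figure may never be addressed, although the expansion patients are the ones who could address it.

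**Working it through.** **1. The plan's own figures.** The documents give no operating characteristics for DLTs. The size of 16 comes from the Simon design (16, continue if 2 or more respond, then 25, reject at 5 or more). Exact binomial calculation gives type I error 0.095, power 0.903 and early stopping 0.515, against the stated 10%, 90% and 0.51. The total also reproduces: 30 + 20 + 18 = 68. The 10 added patients imply 16 − 10 = 6 already at the dose, but neither 6.5 nor 6.7 requires them. The minimum under the BCAD route is 1, so 16 − 1 = 15 can follow.

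**2. Passages side by side.**

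| Question | One place | Another place |
|---|---|---|
| Routes to expansion | Section 4, 6.7: MTD or BCAD | 6.1.1: also highest exposure |
| Patients before expansion | 14.3, SAP 5: six implied | 6.5, 6.7: no minimum |
| Who counts for the MTD | Synopsis: any six evaluable at the dose | 6.4: six escalation patients |

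**3. Size.** The documents give only 18%; every other true DLT rate p below is an assumption, shown as a range.

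- One patient without a DLT: 1 − p. This is an upper bound on clearing the cohort, because any related Grade 2 or higher AE in Cycle 1 also converts it.
- Rolling Six clearance (0 of 3, or 1 of 3 then 0 of 3): (1 − p)³ + 3p(1 − p)² × (1 − p)³.
- Fewer than two in six: (1 − p)⁶ + 6p(1 − p)⁵.
- Two or more by the sixth patient, given none in the first: 1 − (1 − p)⁵ − 5p(1 − p)⁴.
- Expected DLTs in 15 further patients: 15p.

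| p | 1 patient | Rolling Six | <2 of 6 | ≥2 by sixth, given none in first | Expected in 15 |
|---|---|---|---|---|---|
| 18% | 0.82 | 0.75 | 0.70 | 0.22 | 2.7 |
| 25% | 0.75 | 0.60 | 0.53 | 0.37 | 3.75 |
| 33% | 0.67 | 0.43 | 0.36 | 0.53 | 4.95 |
| 40% | 0.60 | 0.31 | 0.23 | 0.66 | 6.0 |
| 50% | 0.50 | 0.17 | 0.11 | 0.81 | 7.5 |

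At 33%, the fifth column is 1 − 0.135 − 0.332 = 0.53.

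**4. What the counts can say about 18%.** The exact one-sided 95% upper limit is 1 − 0.05^(1/n) for zero DLTs. Otherwise it is the p at which the chance of x or fewer DLTs is 0.05.

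| DLTs / n | Upper limit |
|---|---|
| 0/1 | 95% |
| 0/6 | 39% |
| 1/6 | 58% |
| 0/16 | 17.1% |
| 1/16 | 26% |
| 1/25 | 17.6% |

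With zero DLTs the limit falls below 18% only when n exceeds ln 0.05 / ln 0.82 = 15.1, so at 16 patients.

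**5. Denominator.** Section 6.2.1 calls a patient evaluable after 75% of Cycle 1 doses, or after a DLT in that cycle. Neither Protocol 14.4 nor SAP 7.3 has a matching population. A percentage over All Treated counts under-dosed patients without a DLT as non-events, which pulls the rate down.

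**The case against.** The strongest reply is that the one-patient case is a permitted edge, not the planned path, and that it is supervised. This largely stands. A BCAD requires the SRC to see no safety concern, and expansion is the SRC's choice. A RECIST response is first assessed around the start of Cycle 3, so the single patient brings about two cycles of safety data. Reviews during expansion are mandatory, and the Charter, which was not available, may hold numeric criteria. Section 6.11 also takes individual patients off treatment for a DLT.

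Three stronger readings are tempting, and the documents do not support them.

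- A reader might infer that expansion DLTs are never estimated. They are: Protocol 14.5.1 tabulates the number and percentage with a DLT by dose level in All Treated and lists first-cycle DLTs by cohort within each phase. SAP 7.14.1 keeps a first-cycle summary.
- A reader might infer that no MTD can exist if titration never converts. Section 6.1.1 lets the SRC convert, or enrol up to six, without a Grade 2 event, and the Synopsis definition is not limited to escalation patients. The MTD may stay undefined; it need not.
- A reader might take 1 − 0.36 = 64% as the chance that the dose fails the six-patient count. That is unconditional. In this scenario the first patient has had no DLT, so 53% applies. Nor is 67% the chance of expansion, which also needs activity and an SRC decision.

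It can also be said that Section 14 plans no confirmatory inference, so no upper limit has to fall below 18%. That is correct, and the limits above are descriptive. But a hypothesis with a number in it still needs an estimate and a statement of its precision.

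**Conclusion.** The point holds in a limited form. The BCAD route lets up to 15 patients follow one, subject to SRC judgement, while the sample-size text supposes six. The routes to expansion and the two MTD definitions contradict each other. Neither the protocol nor the SAP states a numeric cohort-level DLT boundary for expansion, and the tabulated DLT incidence has no evaluable denominator, interval or criterion against 18%.

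At an assumed 33% DLT rate, the single patient has no DLT with probability 0.67, about 5 DLTs are expected in the next 15, and two or more DLTs by the sixth patient have probability 53% given none in the first. These figures rest on independent patients with a common rate. They say nothing about how often the SRC would choose this route or what its Charter contains. Six patients cannot support a rate below 18%; pooled counts of 0/16 or 1/25 could, but 1/16 could not.

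The documents do not support saying that expansion is unmonitored or that its DLT data go unused.

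**What to change.** (a) Reconcile Protocol 6.1.1 with Section 4 and 6.7 on the routes to expansion, and 14.3 (with SAP 5) with 6.5 and 6.7 on how many patients a dose must have before it is expanded.

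(b) Reconcile the MTD definitions in the Synopsis and 6.4, so that it is clear whether expansion patients count. State in the protocol, or cite from the Charter, which cohort-level DLT criterion governs expansion. What that criterion should be is for the sponsor and the SRC; none is proposed here.

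(c) In Protocol 14.5.1 and SAP 7.14.1, report at each expanded dose the first-cycle DLT proportion over all DLT-evaluable patients, escalation plus expansion, with an exact 90% CI beside 18%. The upper end of that interval is the one-sided 95% limit used above.

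The DLT count itself depends on the missed-dosing item, which reads more than 7 days in the Synopsis and fewer than 7 in 6.3.2. Those passages must also be reconciled before (c) can be produced.

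The cost is protocol wording and one extra table, with no additional patients.
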